Our ultimate goal is to determine whether an individually prescribed homeopathic medicine has an effect greater than a placebo and is a viable treatment option to improve fatigue and quality of life for patients suffering from the symptoms of Post-acute COVID-19 Syndrome. We hope to achieve this goal by conducting a clinical trial that is scientifically rigorous and clinically relevant. Because such a trial would be costly, we first need to do a pilot study that demonstrates our ability to conduct a fullscale trial successfully. Expected results of this pilot study will be to obtain sufficient experience and preliminary feasibility data to justify a larger clinical trial of this hypothesis.

Technical Objectives

Our objectives for the study are to: 1) identify efficient means of recruiting subjects, 2) test and refine our initial study design and treatment protocol, 3) evaluate the instruments for assessing treatment outcomes, 4) estimate sample sizes that will be required in the full-scale trial, 5) determine which homeopathic medicines are most often prescribed for this syndrome, and 6) determine whether there is a measurable effect size difference or positive trend in reduction of symptoms in patients treated with homeopathy.

Methods

Overview: In this double-blind pilot study, 66 patients who have tested positive for COVID-19 and

who have had unexplained fatigue for at least 60 days, as well as at least one other symptom of Postacute COVID-19 syndrome will be randomized to one of two treatment arms: classical homeopathy or placebo. Treatment will be provided by trained homeopathic practitioners, who will see the patients at 4 week intervals over the course of 12 weeks. Fatigue scores and general health status as measured by the SF-36 will be measured at entry to the study and at 4 week intervals for 12 weeks. The MYMOP score of specific symptoms will be administered at entry to the study and at the end of 12 weeks.

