Randomization and blinding: Subjects in the study will be randomly assigned to receive individualized homeopathic treatment or placebo (1 : 1). After the confirmation of eligibility, subjects will be randomized with concealment. Every subject will be assigned with a number and a third party will randomize the subjects to each of the 2 study groups using computer generated random numbers. Randomization will be stratified by age (< or > 50) and duration of Long Covid symptoms (< or > 6months), in permuted blocks of four or six. Randomization will be known only to the homeopathic pharmacist, who will not break the code until after treatment of each subject is completed. An exception to this will be when a research subject suffers an unexplained severe event. In such a case, the randomization code will be broken and the subject withdrawn from the study.

Follow-up: Subjects will have follow-up visits by video with the homeopathic practitioners at 4, 8, and 12 weeks following the initial consultation. At each of these visits, the patients will be reevaluated, adverse side effects will be inquired about, and the classical homeopathic prescription will be renewed or revised, which will again be filled by the homeopathic pharmacist and mailed to the subjects. Although the specific homeopathic prescription might change, subjects randomized to each group will continue to receive placebo or active medicines throughout the study.

The subjects will also complete online questionnaires at 4, 8 and 12 weeks after the initial visit to

evaluate outcomes. At the end of the 12 week study period, those subjects who received placebo will be given the option to receive a verum homeopathic medicine and an additional follow-up visit after 6 weeks will be scheduled for them.

Outcomes:

The primary outcome measurements:

- Fatigue Assessment Score (FAS) at baseline, week 4, week 8 and week 12
- General health status, using the SF-36 at baseline, week 4, week 8 and week 12 Secondary outcome measurements:
- Measure Yourself Medical Outcomes Profile (MYMOP), in which each patient chooses the two most bothersome symptoms to record and follow (at study entry and at the end of 12 weeks)
- The number of subjects who have FAS ≤ 21 will be compared at week 4

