Analysis: Because this is a pilot study with a small sample size, statistical tests are unlikely to reveal any statistically significant differences. However, the data will be summarized and analyzed as if this were a full-scale trial in an intention to treat analysis by the study statistician.

- Demographic data and baseline features will be compared using independent sample t-test and chi-square test for continuous and categorical variables respectively. (Age, sex, duration of symptoms, co-morbidities)
- Missing values will be handled by single imputation by last observation carried forward to handle missing data at the analytical stage.
- The Fatigue assessment scale (FAS) and the SF-36 (8 domains) from baseline (Day=0) and at 4-, 8-, and 12-week follow up will be analyzed by repeated-measure analysis of variance (treatment x time interaction).
- The Measure Yourself Medical Outcomes Profile (MYMOP) collected at baseline and at week 12 will be analyzed by independent sample t-test if normal or Wilcoxon ran sum test if not.
- The proportion of subjects who 'return to normal' (ie have FAS ≤21) will be compared at week 4 with chi-square test.
- Analyses will be performed using SPSS software, version 26. Two-tailed P < 0.05 will be used to denote statistical significance.
- Evidence of non-significant trends will be noted, and the variability of the FAS will be used for sample size estimation for the full-scale trial.

All modifications to this study will be approved by the Human Subjects Committee. Any adverse

event that occurs temporally related to participation in the study will be documented, whether or not it is considered to be related to the homeopathic medicines. Serious and unexpected adverse experiences will be immediately reported by telephone to the Human Subjects Committee.

References

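### The MYMOP analysis does not say whether the week-12 score or the change is tested, does not adjust for baseline, and lets an undefined normality check choose the test

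*Combined protocol and SAP*

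**What the plan says.** In the combined protocol and SAP, Methods, Outcomes, MYMOP is listed as a secondary outcome in which "each patient chooses the two most bothersome symptoms to record and follow (at study entry and at the end of 12 weeks"). The Overview gives the same two time points: "The MYMOP score of specific symptoms will be administered at entry to the study and at the end of 12 weeks".

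The whole MYMOP analysis is one bullet under Analysis: the scores "collected at baseline and at week 12 will be analyzed by independent sample t-test if normal or Wilcoxon ran sum test if not". The bullet does not state:

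- whether the value compared between arms is the week-12 score or the change from baseline;
- how normality will be judged;
- which effect estimate or interval will be reported;
- any model that adjusts for baseline MYMOP.

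The repeated-measures ANOVA in the same section covers FAS and the SF-36 only. The significance rule is general: "Two-tailed P < 0.05 will be used to denote statistical significance".

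**The concern.** An independent-samples test takes one value per patient, but each patient has two MYMOP scores. If the week-12 score is used, baseline is left out of the comparison. If the change is used, baseline is subtracted with a fixed weight of 1. Neither uses baseline with the weight that the data support, so both leave avoidable variance in the treatment comparison.

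The two readings can also give different answers. Their estimates differ by exactly the chance difference in mean baseline MYMOP between arms, and nothing in the plan stops the choice being made after the data are seen.

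A second choice sits on top of this one. The t-test addresses a difference in means and the rank-sum test addresses a rank comparison. An unspecified look at the trial's own data decides which is reported, so the effect measure is not fixed in advance. At stake are a clear, interpretable MYMOP estimate and part of the precision that the collected baseline could supply.

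**Working it through.** **Plan's own figure.** There is none to reproduce. The documents give no effect size, SD, correlation or power for MYMOP.

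**Inputs from the documents.**
- Total sample: "66 patients who have tested positive for COVID-19" (Methods, Overview).
- Allocation: "randomly assigned to receive individualized homeopathic treatment or placebo (1 : 1") (Randomization and blinding), so 66/2 = 33 per arm.
- Two-sided alpha 0.05 (Analysis).

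**Assumptions, not in the documents.**
- Equal SDs at the two visits, set to 1.
- Baseline/week-12 correlation r of 0.3, 0.5 or 0.7.
- A true difference of 0.5 SD.
- Complete data.

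**Step 1: variance of the arm difference, relative to a week-12-only comparison.**
- Week-12 score: 1
- Change score: 2(1 - r)
- Baseline-adjusted week-12 score: 1 - r²
- Adjusted relative to change: (1 - r²) / [2(1 - r)] = (1 + r)/2

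| r | Change, 2(1 - r) | Adjusted, 1 - r² | Cut vs week 12 (r²) | Adjusted / change, (1 + r)/2 | Cut vs change |
|---|---|---|---|---|---|
| 0.3 | 1.40 | 0.91 | 9% | 0.65 | 35% |
| 0.5 | 1.00 | 0.75 | 25% | 0.75 | 25% |
| 0.7 | 0.60 | 0.51 | 49% | 0.85 | 15% |

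For any r strictly between 0 and 1, the adjusted variance is below both alternatives. At r = 0.3 the change score is worse than using week 12 alone.

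**Step 2: power.** Two-sample noncentral t, 33 per arm, 64 degrees of freedom, with standardized difference 0.5 / sqrt(relative variance). The small cost of estimating the covariate slope is ignored.

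| r | Week 12 only | Change | Adjusted |
|---|---|---|---|
| 0.3 | 0.5/√1 = 0.500: 52% | 0.5/√1.40 = 0.423: 39% | 0.5/√0.91 = 0.524: 55% |
| 0.5 | 0.500: 52% | 0.5/√1.00 = 0.500: 52% | 0.5/√0.75 = 0.577: 64% |
| 0.7 | 0.500: 52% | 0.5/√0.60 = 0.645: 73% | 0.5/√0.51 = 0.700: 80% |

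**Step 3: how far the two readings can differ.** The week-12 and change estimates differ by the baseline difference between arms. By chance alone this has standard error sqrt(2/33) = 0.246 SD, about half of the 0.5 SD effect assumed above.

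**Step 4: the normality switch.** Simulated with no treatment effect, 33 per arm, 8,000 trials per scenario. The plan names no normality check, so a Shapiro-Wilk check at 0.05 in each arm was assumed.

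| Data | Rank-sum branch taken | Type I error, two-stage |
|---|---|---|
| Normal | 9.6% | 5.0% |
| Moderately skewed (gamma, shape 4) | 74.6% | 5.4% |

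The Monte Carlo standard error near 5% is sqrt(0.05 × 0.95 / 8000) = 0.24 percentage points. Under this assumed check, the branch taken depends strongly on the shape of the data, while the error rate hardly moves.

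**The case against.** The strongest reply is that the bullet names both visits, so it can be read as a t-test on change, which does use baseline. That is correct. A reader might infer that the plan ignores baseline MYMOP, and the documents do not support that. They support only that the variable is unspecified and that no adjustment is planned. The reply does not remove the point, because the change score is also less precise than adjustment at every r considered.

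A reader might also infer that choosing the test from the data inflates the false-positive rate. The simulation gives no material sign of that, so the objection stands: the harm is an effect measure that is not fixed, not lost error control.

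It is tempting to argue that self-chosen symptoms make baseline scores vary widely and so make adjustment especially valuable. The documents do not settle this. Choosing the most bothersome symptoms could equally bunch baseline scores at the severe end and lower r.

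Finally, MYMOP is secondary, and the plan says "Because this is a pilot study with a small sample size, statistical tests are unlikely to reveal any statistically significant differences". The full-scale sample size is to rest on FAS variability, not MYMOP. This limits the severity. It does not dispose of the point, because the Analysis section also commits to analysing the data as a full-scale trial would, and the Technical Objectives include evaluating the outcome instruments and looking for a measurable effect size. An adjusted difference with an interval serves both aims better than a p-value from a test picked by the data.

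**Conclusion.** The point holds as a minor-to-moderate weakness in the analysis of a secondary outcome. The tested variable is not defined, no baseline adjustment is planned, and the effect measure depends on an undefined normality check.

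The gain from adjustment depends on r and on which reading was meant. At the assumed 0.5 SD difference, it runs from about 4 percentage points of power (week-12 reading, r = 0.3: 52% to 55%, or 51.6% to 55.5% before rounding) to about 28 points (week-12 reading, r = 0.7: 52% to 80%). Against a change score it runs from about 16 points at r = 0.3 to about 7 at r = 0.7. A single summary such as 66 patients acting like 66/0.75 = 88 is true only at r = 0.5 and should not be read as a property of this trial. No trial conclusion is threatened.

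**What to change.** Replace the MYMOP bullet with a single prespecified analysis:

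- Fit a linear model of the week-12 MYMOP score on arm, baseline MYMOP and the two randomization factors (age group and symptom duration).
- Report the adjusted difference between arms with a 95% confidence interval.
- Remove the normality check as a switch between tests.
- Keep the rank-sum test, applied to change from baseline, as a sensitivity analysis only.

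This is a free improvement. It changes the plan's wording and uses a standard model available in SPSS. It needs no new data, visits or patients. Revising the repeated-measures analysis of FAS and SF-36 would not cover it, because MYMOP is outside that model.

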Recruitment: Subjects will be recruited from advertisements on Facebook. We hope to enroll 15-20 patients per month during the 4 month enrollment period. We will use an online survey to screen potential subjects to determine eligibility. Those who are eligible will be scheduled for a telephone screening appointment, during which eligibility will be confirmed and informed consent will be obtained using a consent form approved by the Southwest College of Naturopathic Medicine Human Subjects Committee. Baseline questionnaire data will be collected, including the Fatigue Assessment scale (FAS), the SF-36 quality of life survey, and the Measure Yourself Medical Outcomes Profile (MYMOP).

Eligibility: Patients entered into the study will be ages 18-64 and have a confirmed diagnosis of COVID-19 by previous PCR testing. They will also have a history of persistent, unexplained fatigue for at least 60 days since diagnosis of COVID-19, one other symptom consistent with the syndrome, and a FAS score of 22 or above. Subjects must also have adequate cognitive function to be able to give informed consent and be technologically competent to complete online forms and perform video calls. They must also be willing to fill out regular questionnaires and to use homeopathic medications.

Exclusions: Patients taking steroids, immunosuppressives, or opioid analgesics or who have opioid or other substance dependence and/or are undergoing treatment for substance abuse will be excluded from the study. Patients who were treated in an Intensive Care Unit for Covid-19 and those with concurrent health problems such as active cancers, clinically significant kidney, heart, or hepatic impairment will be excluded. Those diagnosed prior to COVID-19 infection with chronic fatigue syndrome, fibromyalgia, Lyme disease, or chronic psychiatric or neurological illness will also be excluded. Also excluded will be women with suspected or confirmed pregnancy and those who are breastfeeding, those who are enrolled in another trial. Those who are currently being treated by a homeopathic practitioner will also be excluded as well as those who have started a new medication or treatment for Post-acute Covid-19 within the past two months.

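### The analysis plan will note undefined non-significant trends across nine unadjusted primary tests and specifies no effect estimate or confidence interval, although objective 6 asks for an effect size

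*Combined protocol and SAP*

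**What the plan says.** Hypothesis/Purpose gives the reason for the pilot: "we first need to do a pilot study that demonstrates our ability to conduct a fullscale trial successfully". The expected result is to "obtain sufficient experience and preliminary feasibility data to justify a larger clinical trial of this hypothesis".

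Technical Objectives lists six aims. The first five concern recruitment, design and treatment protocol, instruments, sample size and the medicines prescribed. The sixth is to "determine whether there is a measurable effect size difference or positive trend in reduction of symptoms" in patients treated with homeopathy.

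Outcomes names FAS and SF-36 as primary, and MYMOP and the number with FAS of 21 or less at week 4 as secondary. All four measure efficacy.

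Analysis warns that a study of this size is unlikely to produce significant results, then analyses the data as for a full-scale trial at two-tailed P < 0.05. FAS and the eight SF-36 domains go into repeated-measures analysis of variance (treatment by time), and missing values are carried forward. The last bullet says "Evidence of non-significant trends will be noted" and adds that the variability of FAS will be used to size the next trial.

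**The concern.** Three features combine badly.

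- **A trend has no definition.** The plan sets no P-value range, minimum difference, direction or lead outcome. Whoever reads the results can decide afterwards what qualifies, over nine primary tests and about eleven in all, with no multiplicity adjustment.
- **What objective 6 needs is not planned.** A treatment-by-time test over four visits has three degrees of freedom. It gives a P-value, but neither a direction nor a single difference. No effect estimate or interval is specified anywhere.
- **The feasibility side has no matching summary.** Enrolment rate and retention are not outcomes. Because missing values are carried forward, the outcome tables could look complete whatever the dropout.

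The report could therefore describe chance findings as encouraging, show no measure of their imprecision, and give no prespecified account of enrolment or follow-up.

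**Working it through.** **The plan's own figure.** The sample size is 66 (Methods, Overview), allocated 1:1 (Randomization and blinding), so 33 per arm. It cannot be reproduced, because no effect size, SD, power or dropout is given. It is consistent with the hoped-for recruitment: 15 × 4 = 60 to 20 × 4 = 80.

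**Is the plan's expectation of non-significance reasonable?** Largely, yes. For a simple comparison of two means at 33 per arm, power is about 23% at a standardised difference of 0.3, 53% at 0.5 and 81% at 0.7. The difference detectable with 80% power is (1.96 + 0.84) × √(2/33) ≈ 0.69.

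**How often would a trend appear by chance?** From the documents: 1 FAS test + 8 SF-36 domains = 9 primary tests; MYMOP and FAS ≤ 21 bring this to about 11. Assumed: the definition of trend and the correlation between outcomes.

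With no effect, one outcome gives a favourable result
- with 0.05 ≤ P < 0.10 with probability (0.10 − 0.05)/2 = 0.025;
- with 0.05 ≤ P < 0.20 with probability (0.20 − 0.05)/2 = 0.075.

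For nine independent outcomes, the chance of at least one is
- 1 − (1 − 0.025)^9 = 0.204;
- 1 − (1 − 0.075)^9 = 0.504.

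For equally correlated normal test statistics, numerical integration gives:

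| Correlation | 0.05 ≤ P < 0.10 | 0.05 ≤ P < 0.20 |
|---|---|---|
| 0 | 20% | 50% |
| 0.3 | 18% | 42% |
| 0.5 | 17% | 36% |
| 0.7 | 14% | 29% |

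FAS alone gives 2.5% and 7.5%, so most of the chance comes from the number of outcomes. These figures treat each outcome as one directional between-group comparison, which stands in for the planned treatment-by-time test.

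**What would an interval show?** The 95% half-width for the FAS difference is t(64) × SD × √(2/33) = 1.998 × SD × 0.2462. The documents give no SD, so a range is assumed:
- SD 5: ±2.5 points;
- SD 7: ±3.4 points;
- SD 9: ±4.4 points.

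This counts all 33 subjects in each arm; fewer observed values would widen it.

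**Can the feasibility measures be estimated?** If 66 subjects enrolled in the 4 months, the rate would be 66/4 = 16.5 per month. The exact Poisson 95% interval for the count is 51.0 to 84.0, or 12.8 to 21.0 per month. For illustration only, if 53 of 66 had an observed week-12 FAS (80%), the Wilson 95% interval would be 69 to 88%.

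**The case against.** The strongest reply is that the plan is candid and modest. It says in advance that significance is unlikely. It only notes trends, and the one result to which it gives a use in the next trial is the variability of FAS. Five of the six objectives concern feasibility or design. All of this stands, and it rules out several stronger readings.

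- A reader might infer that the decision to proceed rests on a positive trend. No passage says so. Objective 6 makes a trend something to look for, but no progression rule is tied to it.
- A reader might infer that trends are the only evidence carried forward. The same sentence carries FAS variability forward.
- A reader might put the chance of a false trend at 30 to 60%. That range needs a favourable P < 0.20 on any of nine measures, and it also counts significant results, which are not non-significant trends. The upper end further assumes that FAS and the SF-36 domains are uncorrelated within the same patients.
- A reader might conclude that feasibility measures should replace FAS and SF-36 as primary outcomes. That is a debatable trade-off, and the documents do not compel it.

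It is also fair to say that the enrolment interval above covers the whole 15 to 20 range, so it could not separate recruitment on target from a modest shortfall. It would still show a large one.

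The reply does not explain why an undefined trend is preferable to an estimate with an interval, when objective 6 asks for an effect size.

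**Conclusion.** The point holds as a cheap improvement to the analysis plan; it is not a flaw that undermines the pilot. Noting undefined trends over nine unadjusted primary tests leaves the rate of chance trends uncontrolled: about 14 to 20% under a strict definition and 29 to 50% under a lenient one, for correlations of 0.7 to 0. The definitions, the correlations and the directional test are assumptions, and the width of the range itself follows from the plan's silence. An estimate with its interval answers objective 6 directly and shows how little 33 per arm can say: about ±2.5 to ±4.4 FAS points for an assumed SD of 5 to 9. The documents do not support the further claim that the sponsor will decide on a full-scale trial from a trend.

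**What to change.** 1. In Analysis, replace the trends clause with: *The between-group difference in FAS at week 12, and in each SF-36 domain, will be reported with its 95% CI, and a non-significant difference will not be described as a trend.* Keep the rest of the sentence, on FAS variability and sample size.
2. Change objective 6 to: *estimate the effect size with its 95% CI*. Otherwise it would still ask for a trend that the analysis no longer reports.
3. Alongside the existing outcomes, not in place of them, report enrolment per month against the stated 15 to 20, and the share of subjects with an observed (not carried-forward) week-12 FAS, each with a 95% CI.

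This needs no new visits, subjects or instruments. The costs are Human Subjects Committee approval, which the protocol requires for any modification, and efficacy results that are presented openly as imprecise estimates.
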